**Secondary:**

- 1) Does the effectiveness of PARTICS differ by race/ethnic group (AA vs. H/L).
- 2) Does the effectiveness differ by smoking status?

**Exploratory:** How do patient characteristics and patient reported barriers influence PARTICS' effectiveness?

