**Study Aims:**

Working with patient & health system stakeholders, we will conduct a pragmatic real-life study in a population of African American and Hispanic/Latino adults disproportionately impacted by asthma.

**Specific Aim 1:** To assess whether a Patient Activated, Reliever-Triggered Inhaled CorticoSteroid (PARTICS) strategy can reduce asthma morbidity in this population.

- Our primary outcome will be asthma exacerbations which have been shown to be important to patients and healthcare stakeholders.
- Our secondary outcomes will include additional outcomes important to patients such as days lost from work or school, asthma control, and asthma related quality of life.

**Specific Aim 2:** To examine whether the effectiveness of a Patient Activated, Reliever-Triggered ICS (PARTICS) strategy differs between African American or Hispanic/Latino adults or by smoking status.

**Exploratory Aim:** To examine, whether particular patient clinical characteristics (e.g. prior exacerbations) or specific barriers to adherence (e.g. beliefs, depression) impact the effectiveness of a PARTICS approach in these populations.

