appears that the majority that responds has a type of inflammation that is closely associated with eosinophils and is labeled Type 2 inflammation (Fahy 2015, Peters 2014). While this area is evolving, a recent review has suggested that blood eosinophils may be one of the best biomarkers to identify patients likely to respond to ICS or therapies directed at Type 2 patients (Pavord 2017). There has been enthusiasm about blood eosinophils since the sample is easily obtainable and the assay is available in ANY clinical laboratory. We will determine whether peripheral blood eosinophil count serves as an effect modifier of the relationship between treatment (PARTICS vs. usual care) and the study's primary outcome (number of asthma exacerbations per year). We will stratify participants based on a pre-specified peripheral blood eosinophil count threshold of 300/uL. This threshold is based on a frequently-used cutoff for 'eosinophil-high' status in the anti-eosinophil therapy literature (Giannetti 2016).

As discussed in section **III.E, Biostatistical analysis**, we will be adequately powered for both these subgroup analyses.

Additional exploratory subgroup will be considered including the following factors: 1) modality in which questionnaires have been returned; 2) patients' attitude towards ICS from the validated BMQ (skeptical (low necessity, high concerns), indifferent (low necessity, low concerns), ambivalent (high necessity, high concerns), accepting (high necessity, low concerns)); 3) presence of depressive symptoms (yes/no); 4) health literacy status (low or marginal versus high); and 5) Discrimination stressors from the everyday discrimination scale (SHORT).

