## 6. Subgroup Analysis

Subgroup analyses for the primary efficacy outcome will be performed on the ITT population in order to explore whether the treatment effect is consistent across subgroups. Our goal is to determine the impact of PARTICS on asthma exacerbations in two pre-specified main subgroups determined by 1) race/ethnic group (African American vs. Hispanic/Latino) and 2) smoking status [i.e., participants who are previous (>10 pack- years)/current (or within 1 year) smokers vs. those who have not smoked (in the past year and <10py)] 3) patients with high FeNO vs. low and 4) patients with high eosinophil counts vs. low. Based on our prior experience, about 50% of our population will be smokers or ex- smokers.

Subgroup analyses to evaluate variation in treatment effect will be performed on the basis of tests for interaction using the same Andersen-Gill version of the Cox proportional hazards model as used in the primary analysis. The model will be including terms for treatment arm, subgroup, and treatment by sub-group interaction and adjust for all variables included in the primary model. Additionally, treatment effects within each categorical subgroup will be examined separately using analogous Andersen-Gill model. Event rates by treatment arm and hazard ratios with 95% confidence intervals will be reported for each subgroup. Forest plots will be generated displaying the estimated hazard ratios and 95% confidence intervals for each subgroup will be presented. Variation in treatment effect will be assessed on the basis of tests for interaction in the Andersen-Gill version of the Cox proportional hazards model described above. Treatment effects estimated within each categorical subgroup will be considered exploratory/hypothesis generating. Thus, no adjustment for multiple testing will be employed.

Additional exploratory subgroup analyses will be performed investigating the effect of the following factors: 1) modality in which questionnaires have been returned; 2) patients' attitude towards ICS from the validated BMQ (skeptical (low necessity, high concerns), indifferent (low necessity, low concerns), ambivalent (high necessity, high concerns), accepting (high necessity, low concerns)); 3) presence of depressive symptoms (yes/no); 4) health literacy status (low or marginal versus high); and 5) patient adherence barriers from the validated ASK12 questions 1,2,3 and 11 related to measures of inconvenience, forgetting and

cost.

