## **8. Sample Size and Power Considerations**

Sample size and power calculations were performed using PASS software (Hintze 2011), using the similarity of inference between the Andersen-Gill models and Poisson regression.

For the primary efficacy outcome, power calculations were based on an estimated primary event intensity of 0.4 per year (0.5 per 15 months) in the control arm (as seen in the BELT study), 15 months of follow-up for each individuals with an annualized rate of uniform loss to follow-up of 25% (31.25% in 15 months of follow-up) and a two-sided significance level of 0.05. With these assumptions, 1200 up to patients (600 per arm) yields 80% power to declare a reduction of 23.5% in the intensity of exacerbations as statistically significant. Even if the event rate were lower at .35 we would still have 80% power to detect a 25% difference. This difference is clinically meaningful and is well within the 25-50% (and more likely 40-50%) (O'Byrne 2006, Rabe 2006, Buhl 2012, Papi 2013, Calhoun 2012) reductions noted with such studies.

For subgroup analysis, using these same assumptions, with group size of 600 (300/arm), at a power level of 80% we would be able to detect an expected change of 32%, still well within the noted effects.

Power for secondary outcome comparisons were also calculated. Based on results observed in the BELT study, we expect the standard deviations in ASUI scores to be 0.23 in each arm. Thus, we will have 80% power to detect a difference of 0.04 in ASUI scores between treatment arms. Assuming standard deviations of 4.9 in each treatment arm on the ACT questions score, we will have 80% power to detect a difference of 0.96 in ACT scores.

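### The subgroup power claim rests on a within-subgroup figure (32% at 300 per arm); no power is given for the interaction test that answers Specific Aim 2

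*Combined protocol and SAP*

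**What the plan says.** Four parts of the combined protocol and SAP bear on this.

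- **Section II, Participant subgroups (Full study only)** states that "we will be adequately powered for both these subgroup analyses" and refers to III.E for support. The same section says that African American and Hispanic/Latino patients will be analysed separately.
- **Section III.E.8, Sample Size and Power Considerations**, gives one subgroup figure: "with group size of 600 (300/arm), at a power level of 80% we would be able to detect an expected change of 32" per cent.
- **Section I.A.2** sets the question. Specific Aim 2 is "To examine whether the effectiveness of a Patient Activated, Reliever-Triggered ICS (PARTICS) strategy differs between African American or Hispanic/Latino adults or by smoking status", and the first secondary research question is "Does the effectiveness of PARTICS differ by race/ethnic group (AA vs. H/L"); the second asks the same for smoking.
- **Section III.E.6, Subgroup Analysis**, gives the method. It names "two pre-specified main subgroups determined by 1) race/ethnic group (African American vs. Hispanic/Latino") and smoking status, then lists FeNO and eosinophil groups as well. It says "Subgroup analyses to evaluate variation in treatment effect will be performed on the basis of tests for interaction" in the Andersen-Gill model. It also plans separate models within each subgroup, but "Treatment effects estimated within each categorical subgroup will be considered exploratory/hypothesis generating". It expects that "about 50% of our population will be smokers or ex- smokers".

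**The concern.** The adequacy statement and the figure behind it refer to a different analysis from the one that answers Aim 2. Detecting a 32% reduction among 600 patients is a question about one subgroup. Whether the effect differs between two subgroups is a question about the ratio of two hazard ratios, and the variance of its logarithm is the sum of the two subgroup variances. Power for the first question says little about power for the second.

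This matters because the plan itself gives reasons to expect a difference. Section II cites a study in which Hispanic/Latino patients seemed to gain less from a similar approach, and it cites weaker responses to inhaled corticosteroids in smokers. If the trial is described as adequately powered for its subgroup analyses, a non-significant interaction may be read as evidence that the benefit is consistent, when the test may have had little chance of showing a real difference.

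**Working it through.** **Inputs.** All from III.E.8 unless noted: control rate 0.4 per patient-year; 15 months (1.25 years) of follow-up; uniform loss of 31.25% over that time; two-sided 0.05; Poisson basis; 300 per arm in each subgroup. The 605/605 enrolment target by race/ethnicity in section II and the expected 50% smokers in III.E.6 are consistent with 300 per arm. Two assumptions are mine: the control rate is 0.4 in both subgroups, and there is no overdispersion.

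**Step 1. Exposure.** Mean follow-up = 1.25 × (1 − 0.3125/2) = 1.0547 years. Expected events in an arm = n × 0.4 × 1.0547 × HR, with HR = 1 for control.

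**Step 2. Reproduce the plan's figures.** SE of log HR = √(1/E_control + 1/E_PARTICS); power = Φ(|ln HR|/SE − 1.96).

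- Primary, 600 per arm, HR 0.765: 253.1 and 193.6 events, SE 0.0955, power 80.1%. The plan says 80%.
- Within one subgroup, 300 per arm, HR 0.68: 126.6 and 86.1 events, SE 0.1397, power 78.8%. Other standard Poisson or event-count formulas give 79.3% to 80.3%. With the log-HR formula, 80% is reached at a 32.4% reduction.

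The 32% figure is therefore sound as a within-subgroup effect.

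**Step 3. Interaction test.** SE of the log ratio of hazard ratios = √(sum of 1/E over the four cells). The effect pairs below are illustrations, because the documents give none.

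| Reductions in the two subgroups | Ratio of HRs | SE | Power |
|---|---|---|---|
| 32% vs 15% | 0.80 | 0.192 | 21% |
| 25% vs 0% | 0.75 | 0.185 | 34% |
| 50% vs 25% | 0.67 | 0.205 | 51% |
| 32% vs 0% | 0.68 | 0.188 | 54% |
| 40% vs 0% | 0.60 | 0.192 | 76% |
| 47% vs 0% | 0.53 | 0.196 | 90% |
| 50% vs 0% | 0.50 | 0.199 | 94% |

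Worked example, 32% vs 0%: cells of 126.6, 86.1, 126.6 and 126.6 events; SE 0.188; |ln 0.68|/0.188 = 0.3857/0.1879 = 2.05; Φ(2.05 − 1.96) = 0.537.

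**Step 4. Detectable ratio at 80% power.**

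- Other subgroup at HR 1.00: HR 0.582, ratio about 0.58 (about 42% vs 0%).
- Other subgroup at the design HR of 0.765: HR 0.423, ratio 0.423/0.765 = about 0.55 (about 58% vs 23.5%).

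**Step 5. Precision if there is no difference.** With both subgroups at HR 0.765, SE = 0.191. The expected 95% CI for the ratio is exp(±1.96 × 0.191), about 0.69 to 1.45.

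**Step 6. Sensitivity of the 32% vs 0% case.** Power is 46% if dropouts contribute no follow-up and 61% if there is no loss at all. With a 40:60 smoking split, the low end of the range in section II, it is 51% to 53%. With an assumed overdispersion factor of 1.5, 2.05/√1.5 = 1.68 and power is about 39%.

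**The case against.** The strongest reply is that the sentence can be defended as written. Section II plans to analyse African American and Hispanic/Latino patients separately, III.E.6 plans separate models within subgroups, and for those analyses the 32% figure applies and reproduces. No section claims power for an interaction test. This stands. A reader might infer that the adequacy claim is false for every subgroup analysis; the documents do not support that.

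A second reply is that no single interaction power figure can be pinned on the plan. This also stands. A reader might settle on 54% (32% vs 0%), but the plan offers 32% as a detectable change within a subgroup, never as a difference between subgroups. That pair also averages only a 16% reduction over two equal halves, below the 23.5% design effect. If the whole design effect fell in one half, the pair would be 2 × 23.5% = 47% vs 0%, with 90% power. Against that, section II expects one group to benefit less, not to have no benefit, and graded pairs within or near the cited 25% to 50% range stay low (50% vs 25%: 51%).

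Third, it is uncertain which subgroups the word both refers to. The sentence follows text on FeNO and eosinophils, whereas III.E.6 calls race/ethnicity and smoking the two main subgroups. The second reading is more likely, but it is an inference. III.E.8 gives no figure specific to the FeNO or eosinophil groups, nor an expected split, so the sentence needs clarifying on either reading.

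Fourth, Aim 2 is worded as an examination, III.E.6 makes no multiplicity adjustment, and no decision rule hangs on the interaction p-value. That lowers the severity. It does not supply the missing figure.

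**Conclusion.** The point holds in a limited form. The adequacy statement is supported for detecting about a 32% reduction within a subgroup of about 300 per arm. It is unsupported for the interaction test that answers Specific Aim 2. On the plan's assumptions that test has 80% power only if one subgroup's hazard ratio is about 0.55 to 0.58 times the other's; for the pairs examined, power runs from about 21% to 94%. These figures assume equal control rates, equal subgroup sizes and pure Poisson variation, and the last is the favourable case for recurrent events.

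Low interaction power is common and is not in itself a design fault. A reader might conclude that the trial is too small, but the sample size was set for the primary comparison, whose 80% power reproduces and is unaffected. Severity: minor to moderate.

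**What to change.** Three changes of wording and reporting:

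1. **Section II, Participant subgroups.** Name the subgroups meant, and limit the claim to detecting about a 32% reduction within a subgroup of about 300 per arm.
2. **Section III.E.8.** Label the 32% as a within-subgroup effect. Add the detectable ratio of hazard ratios for the interaction test, about 0.55 to 0.58 at 80% power, with the assumptions behind it.
3. **Section III.E.6.** For Aim 2, report the ratio of hazard ratios with its 95% CI beside the interaction p-value, so that a non-significant result is not taken as evidence of a consistent effect. The section already provides hazard ratios with intervals for each subgroup; this adds the direct comparison.

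No extra patients or data are needed, and the model and primary analysis stay as they are. The only cost is a less favourable power statement for Aim 2.

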## **C. Participant Recruitment, Screening, Enrollment, and Follow-up**

### **1. Eligibility Criteria**

#### **INCLUSION CRITERIA**

- Black or Hispanic based on self-identification (Hispanic if identify as both)
- Male and female, ages 18-75 years
- Ability to provide informed consent
- Clinical history consistent with asthma for > 1 year.
- Prescribed ICS as daily maintenance therapy
- Participant must also have an ACT score of 19 or less, **or** a history of one or more exacerbations in the past year that required patient report of systemic corticosteroid use.

#### **EXCLUSION CRITERIA**

- Life expectancy less than one year
- Known allergy to the ICS inhaler used in the study
- Having COPD or other chronic lung disease other than asthma; with the exception of the following:
  - Dx of COPD in a *never smoker* without any other lung disease or any other disease that might cause airway obstruction such as: Cystic Fibrosis, Connective Tissue Disease, premature birth, organ transplantation, bronchiectasis, sarcoid, and obliterative bronchiolitis
  - Dx of COPD in former smoker with normal PFTs done after the person quit smoking
  - Dx of COPD in current smoker with normal PFTs done in past 24 months

- Dx of COPD IN CURRENT OR FORMER SMOKER with obstruction on PFTs: normal diffusing capacity in past 24 months and demonstrated reversibility of 12% or more *at any time*
- Regular systemic corticosteroid use daily or every other day for any reason—including asthma or other medical reasons
- Use of systemic corticosteroid, or visit to the doctor's office, emergency department (ED) or urgent care, or overnight hospitalization for an asthma exacerbation in the past month (can wait and re-check eligibility after one month)
- Use of biologics (injections or infusion medicines): with the exception of the following:
  - the patient has been on a stable dose of a biologic for at least 6 months and,
    - must have had an exacerbation at least 2 months after starting on a biologic to be considered eligible **OR**
    - must have a current ACT score  $\leq 19$  to be considered eligible.
- Bronchial thermoplasty less than 6 months ago (can re-check eligibility 6 months after procedure)
- Another family member living in the same household already enrolled in study

All sites will initially identify potentially eligible patients through specific searches of their EHR or data repository of EHR data designed to support research. Before contacting any patients, the provider or the practice Medical Director (who has been given permission to recruit on behalf of the practice) gives permission to contact the patient (this is the same for all contact scenarios). When an identified patient does not have a scheduled visit, the research coordinator will send an informational letter about the study that would ask if he/she is interested in hearing more about the study. The research coordinator's information will be listed for the patient to call if interested. Patients who do have a scheduled visit will receive a phone call from the research coordinator giving a brief overview of the study and asking if they would like to hear more about the study during the clinic visit. If the research coordinator was unable to get in touch with the patient by phone the coordinator would approach the patient during the clinic visit (if approved by the medical provider). Patients who are sent a letter and don't respond will be considered opt out. Patients who are called and do not want to learn more about the study will be considered opt out unless they indicate they would like to be contacted a later date. Patients who are seen in the clinic and do not want to participate, will be considered opt out unless indicating that they would like to be contacted at a later date.

Efficacy trials generally include only 5% of eligible asthmatics (Herland 2005, Travers 2007). In contrast, we have set broad eligibility criteria including allowing patients with a COPD diagnosis who meet the following criteria with regard to the COPD diagnosis: patient is a never smoker without any other lung disease or any other disease that might cause airway obstruction such as: Cystic Fibrosis, Connective Tissue Disease, premature birth, organ transplantation, bronchiectasis, sarcoid, and obliterative bronchiolitis; a former smoker with normal PFTs done after the person quit smoking; a current smoker with normal PFTs done in the past 24 months; a current or former smoker with obstruction on PFTs with normal diffusing capacity in the past 24 months and demonstrated reversibility of 12% or more at any time. This study includes smokers and COPD is a common co-diagnosis in patients from communities where smoking is prevalent. This approach is much more pragmatic and inclusive of patients who are likely to benefit from the intervention.

Furthermore, from our BELT study, we know that if we enroll patients on ICS who are not well

controlled using a standard asthma control instrument, or who are on an ICS/LABA, that one third will experience exacerbations over the next year. Additionally, patients with a history of exacerbation are at high risk for others (Miller 2007). In contrast to prior efficacy studies, we are not excluding current smokers (up to 25% of asthmatics), past smokers (10%- 25% of asthmatics and an even higher proportion of those turned away in our prior studies), or those with other comorbidities, or those who use other medications. We exclude only patients who cannot provide consent or who are not able to physically participate. We have included provisions for low literacy by providing oral materials for consent and a voice response system option in English and Spanish for those with limited literacy.

## 2. Recruitment and Screening

The Vanguard process is designed to track with the full study protocol as closely as possible to provide a piloting of the processes. As such participant recruitment will follow all of the methods outlined for the full study, as follows. Participant initial screening will primarily take place through searches of EHR data with an invitation to consider the study coming from the patient's practice. This could be in person at the time of a visit, through a letter, through a phone call or through a secure message in the site's EHR. Sites may use some or all of these techniques as best fits their patient population. For patients that respond with interest the study coordinator will do a brief screening during a real-time interaction, either face to face or via a secure telehealth connection. If the individual remains interested, the patient will then interact with the online enrollment system.

Full study difference: Sites with the ability to enroll patients at home will offer that option to patients who are interested in enrolling.

### (a) Patient Enrollment System (PEERS)-

This system will be identical for the Vanguard process as it is for the full study. See **section II.F** for a description of the uses for this system, called Patient Engaged Electronic Reporting System (PEERS).

## 3. Randomization Scheme

- In the Vanguard study, 36 patients from 4 clinical sites (2 sites enroll AA patients, and the other 2 sites enroll H/L patients). Thirty two English speaking patients will be randomized at the 3:1 ratio (with 6 patients randomized to the intervention arm and 2 patients randomized to the enhanced usual care arm at each site. In other words, the Vanguard randomization scheme will only be stratified by site, and will not be stratified by race/ethnicity. In addition, 4 H/L Spanish speaking patients will be in placed in the intervention group to be able to sufficiently test the intervention materials.
- Full study difference: patients will be randomized stratifying by site, race/ethnicity (AA vs. H/L) using permuted blocks of size 4 and 8 through central randomization available online using the same system which will collect consents. Participants will be randomized in a 1:1 ratio of intervention to enhanced usual care.

